# 2 Trial Design

# 2.1 Trial Procedures – Overview

This trial has an open-label, uncontrolled, single-dose, dose-ascending design and consists of two cohorts, each of 5 patients. Due to the low prevalence of severe and moderately severe haemophilia B patients with a severe phenotype, the trial will be conducted at multiple centres in multiple countries. Since this is a first-in-man single dose escalation trial with a high-risk medicinal product, an adequate information communication system between the sites will be in place (details will be described in the Trial Procedures Manual).

Patients fulfilling the eligibility criteria will be allocated to either Cohort 1 or Cohort 2. Each patient will receive a single dose of IMP (AAV5-hFIX) and will thereafter be followed for five years with respect to safety and with respect to efficacy measured as levels of FIX, bleeding patterns and consumption of FIX replacement therapy. Patients will attend the same visits and undergo the same procedures, regardless of their allocation to Cohort 1 or 2.

Cohort 2 will be initiated based on the recommendation of the data monitoring committee after review of safety data from Cohort 1. These data will include a 12-week follow-up for the first 3 patients dosed as well as four weeks follow-up for the remaining 2 patients in cohort 1 (see figure 2-1). If transaminase elevations requiring corticosteroid treatment have occurred in one or more of the first three patients in Cohort 1, the data monitoring committee may recommend extending the follow-up period, before sponsor decision to initiate Cohort 2 is taken. Inter-cohort stopping criteria are described in the protocol, section 19.2.1

#### Figure 2-1, Inter-cohort Staggering Interval

Within each cohort, there will be an observation period between IMP administration to the 1st and 2nd patient and between IMP administration to the 2nd patient and subsequent patient (fig 2-2). Intra cohort stopping criteria are described in the protocol, section 19.2.1.

Larix A/S - Strictly Confidential F501-0-1–5 SAP Template Page 9 of 34

Date: 27MAY2021

Final no. 05

Page 10 of 34

CT-AMT-060-01 EudraCT No.: 2013-005579-42 Statistical Analysis Plan

- After the 1st patient has been dosed in a cohort, the data monitoring committee will evaluate available safety data collected during a period of minimum 24 hours after IMP administration to this first patient. The data monitoring committee will recommend if and when dosing of the 2nd patient can be initiated.
- After the 2nd patient has been dosed in a cohort, the data monitoring committee will evaluate safety data collected during a period of minimum 24 hours after IMP administration to this second patient. The data monitoring committee will recommend if and when dosing of the subsequent 3 patients can be initiated.
- The dosing of the 3rd, 4th and 5th patient within a cohort must be separated by a minimum of 24 hours to ensure observation of any acute reactions.

Details on an adequate information communication system with and between the sites to ensure the timings of patients dosing within a cohort are adhered to will be described in the Trial Procedures Manual.

#### Figure 2-2, Intra-cohort Staggering Interval

After IMP administration, patients will remain at the clinical site for 24 hours for monitoring of tolerance to IMP and for detection of potential immediate adverse events. Hereafter, patients will be followed with respect to safety and efficacy parameters for 5 years (260 weeks):

- Every week up to week 12
- Every 2nd week from weeks 12 to 26
- Every 13th week from weeks 26 to 156 (6 months to 3 years)
- Every 26th week from weeks 156 to 260 (3 years to 5 years)

Patients on prophylactic FIX replacement therapy will be tapered off their prophylactic FIX replacement therapy in the period from Visit 8 to Visit 14 (weeks 6 - 12). If the investigator determines that FIX replacement therapy should be re-initiated, based on FIX levels or for other reasons, prophylactic FIX replacement therapy may be tapered off again at a later time point. In relation to the withholding of FIX replacement therapy, additional visits may be required for the purpose of additional monitoring of FIX activity levels. For further details, please refer to protocol, section 11.4.

Larix A/S - Strictly Confidential F501-0-1–5 SAP Template Page 10 of 34

Date: 27MAY2021

CT-AMT-060-01 EudraCT No.: 2013-005579-42 Statistical Analysis Plan Final no. 05 Page 11 of 34

During the entire trial period, blood samples will be drawn regularly for measurements of FIX activity and FIX protein concentration in plasma. For patients on prophylactic FIX replacement therapy, attempts should be made to allow blood sampling at time points where FIX activity and FIX protein concentration are expected to be at lowest justifiable levels. For further information, please refer to protocol, section 12.1.1.

Flowcharts for the trial procedures appear in section 5 of the protocol.

# 2.2 Determination of Sample Size

No formal sample size calculation is made. The choice of 5 patients in each cohort is considered sufficient to capture commonly occurring adverse events.

# 2.3 Blinding

The trial is an open-label un-controlled trial where patients are asigned to one of two cohorts. In each cohort one single dose of trial drug (AAV5-hFIX) is administered for each patient. In cohort 1 one single dose of  $5.0 \times 10^{12}$  gc/kg IMP is administered whereas in cohort 2 one single dose of  $2.0 \times 10^{13}$  gc/kg IMP is administered.

# 2.4 Data Pre-processing

A special problem arises in relation to the data originating from the e-Diary (where the patient registers bleeds and administration of FIX replacement therapy), since it is not possible to correct data once entered in the e-Diary data base. For corrections of erroneous e-Diary data when generating the trial data base the Data Management Notes are used. These notes contain comments related to queries on (amongst other data) e-Diary data, but also contains investigator comments on erroneous data from the e-Diary on bleeds and administration of FIX replacement therapy. The Data Management Notes are not part of the trial data base as such but is locked (in the format of an excel file) together with the trial data base when a formal data base freeze is performed. Each of the specific notes are identified by a unique Id number.

Based on the Data Management Notes Larix will incorporate corrections to the data extracted from the trial data base. The corrections are incorporated employing 'hard coding', when the ADaM datasets are generated and will be documented in the ADRG (Analysis Data Reviewers Guide). The corrections to be included will be discussed and verified with the responsible person at uniQure, and the document maintained concerning these corrections is considered a living document until the programming of the final analyses.

Larix A/S - Strictly Confidential F501-0-1–5 SAP Template Page 11 of 34

Date: 27MAY2021

CT-AMT-060-01 EudraCT No.: 2013-005579-42

Statistical Analysis Plan

Final no. 05 Page 12 of 34

# 3 Analysis Sets

# 3.1 Full-Analysis Set

The full-analysis set (FAS) will according to the protocol comprise of all dosed patients and will be used for reporting.

# 3.2 Per Protocol Analysis Set

The Per Protocol (PP) Analysis Set comprises a subset of patients from the FAS population without any major protocol deviations interfering with the analysis of the primary or secondary endpoints.

# 3.3 Safety Analysis Set

The safety analysis set is the same as FAS.

Larix A/S - Strictly Confidential F501-0-1–5 SAP Template Page 12 of 34

4

Date: 27MAY2021

Final no. 05

Page 13 of 34

CT-AMT-060-01 EudraCT No.: 2013-005579-42 Statistic:

Statistical Analysis Plan

# Statistical analyses and presentation of data

# 4.1 General Considerations

All reporting will be made for the Full Analysis Set. Reporting may also be made for other analysis populations (PP Analysis Set), or subgroups of patients based on for example genotype.

Data will be presented in tables and listings following the principles in ICH E3 guideline regarding (structure and content of clinical reports). On the listings, cohort will appear in a separate column and the listings will be sorted by cohort/dose and patient ID within cohort/dose. In the tables data from each cohort/dose will be presented in separate columns. For selected endpoints data will also be presented graphically.

All data will be listed, including unused and spurious data. Imputation of missing or partial data will not be done unless explicitly described. In the case of imputation of missing data, both the original missing or partial data and the imputed values will be listed. Continuous data will be shown in listings with the same precision as captured.

Summary tables will show the number of non-missing values

Numerical data will be presented in summary tables by number of patients, arithmetic mean, median, standard deviation, minimum and maximum and CV (%). Categorical data will be presented by number and percent of patients as well as the number of events (where applicable).

Patient level summaries (listings) will be presented adjusted for observation time where applicable. This includes but is not limited to the annualized rate of selected signs and symptoms and annualized bleeding rate.

In general, laboratory parameters will be presented by visit and will include categorization of parameters into low/normal/high where applicable. For some of the laboratory parameters a measurement of '< x' (x being a numerical value) are occasionally registered. In such a case a value equal to  $0.5^*x$  is used when summary tables are generated, whereas the '< x' will be reported in listings. This recalculation for use in summary tables will also be documented in the ADRG.

The distance in days between a measurement/event and the trial drug administration date is calculated as follows:

- If date(measurement/event) < date(trial drug administration): Distance in days = date(measurement/event) – date(trial drug administration)
- If date(measurement/event) >= date(trial drug administration): Distance in days = date(measurement/event) – date(trial drug administration) + 1

The distance between a FIX activity measurement and the latest FIX replacement therapy administration preceding the FIX activity measurement in question (c.f. section 4.4.2.1) is calculated as follows:

- date(FIX activity measurement) - date(preceding FIX replacement therapy administration) + 1

The date and time of the FIX activity measurement in question and the FIX replacement therapy administrations respectively are used to find the latest FIX replacement therapy administration preceding

Larix A/S - Strictly Confidential F501-0-1–5 SAP Template Page 13 of 34

•
ariv

CT-AMT-060-01 EudraCT No.: 2013-005579-42 Statistical Analysis Plan

Final no. 05 Page 14 of 34

the FIX activity measurement in question. In case the dates of the FIX activity measurement in question and a FIX replacement therapy administration are the same and no time is indicated, it is assumed that the FIX replacement therapy administration precedes the FIX activity measurement in question, and the above defined distance therefore becomes equal to 1 (see also section 4.4.2.1).

Duration of an AE in days is calculated (when possible) as date(Resolution) - date(Onset) + 1.

Date: 27MAY2021

No formal statistical hypothesis will be tested. Two-sided 95% confidence intervals may be calculated but these intervals represent exploratory analyses and will not be related to formal statistical hypothesis tests. No correction for multiplicity will be applied.

# 4.2 Patient Disposition

The data regarding analysis sets (FAS, PP (if defined), withdrawals (and reason for withdrawal), major protocol violations, and previous screening for this trial (yes/no) will be presented in a listing.

The data will also be summarised in a table.

The Sponsor will provide Larix with information on protocol deviations in the format on an excel file according to a pre-specified and agreed structure. Larix will transfer the information to a SAS dataset (SDTM domain DV).

# 4.3 Demographics and other Baseline Characteristics

## 4.3.1 Demography

At the screening visit (Visit 1) the date of birth (i.e. the age at the sceening visit), race, ethnic group, height, weight, and BMI are captured. According to inclusion criterion 1 all patients are males. The data (captured at Visit 1) will be listed and also summarised in a table per cohort and overall.

# 4.3.2 FIX Gene Mutation

At the screening visit available information of FIX gene mutation will be collected. If the information is not available a blood sample for FIX gene sequencing analysis will be collected at visit 1 or at a later time point during the trial. This blood sample can only be collected if a separate informed consent is given by the patient.

The data will be presented in a listing.

# 4.3.3 Medical History and Concomitant Illnesses

At the screening visit relevant medical history and concomitant illnesses will be registred. Bleeding history will be reported separately (c.f. section 4.3.4). Medical history is any previous medical condition or surgical event that started prior to visit 1 (screening), but is not ongoing at visit 1. A concomitant illness is defined as a medical condition ongoing at visit 1.

The data including coding terms from MedDRA (version 17.1) will be presented in a listing.

Larix A/S - Strictly Confidential F501-0-1–5 SAP Template Page 14 of 34

Date: 27MAY2021

CT-AMT-060-01 EudraCT No.: 2013-005579-42 Statistical Analysis Plan Final no. 05 Page 15 of 34

# 4.3.4 History and Status of Bleeding

## 4.3.4.1 Haemophilia B History

At the screening visit data regarding time of diagnosis, FIX activity at diagnosis, latest measured FIX activity (including the date of this measurement), degree of FIX deficiency, history of FIX inhibitors measured to be >= 0.6 BU/mL (Yes/No), and family members with a history of having FIX inhibitors measured to be >= 0.6 BU/mL (Yes/No) will be registered. Time (in years) from the date of diagnosis until Visit 2 (day 1) will be derived.

The data will be presented in a listing, and summarised in a table.

## 4.3.4.2 History of FIX Medication and Bleeding

At the screening visit the following historical data regarding bleeding and FIX treatment are collected:

For all patients:

- Number of exposure days of FIX replacement therapy prior to trial entry. An exposure day is a day where the patient received one or more infusion(s) of a FIX product replacement therapy.

For patients receiving prophylactic FIX replacement therapy:

- Number of months on prophylactic FIX replacement therapy for the last 12 months.
- Dose and frequency of dosing; if the patient is on intermittent prophylactic FIX replacement therapy, each regimen followed in the last 12 months should be reported
- Recombinant or plasma FIX product (registered for each treatment regimen)
- Number of treatment requiring bleeding episodes in the last 12 months during each specific prophylactic treatment regimen
- Average number of units to treat a bleed during each specific prophylactic treatment regimen during the last 12 months
- Number of bleeding episodes prior to initiation of prophylactic FIX replacement therapy

For patients receiving on-demand treatment:

- Number of treatment requiring bleeding episodes in the last 12 months during each specific treatment regiment
- Recombinant or plasma FIX product
- Average number of units to treat a bleed during each specific on demand treatment regimen during the last 12 months

All the data will be presented in listings. All data registered in the trial dat base will be included even if not complying strictly with the requirement of having occurred within one year (365 days) before the screening (Visit 1) date.

Furthermore data on use of FIX therapy in the 7 days preceding visit 1 specifically have been registered.

These data will be presented in a listing.

*Larix A/S - Strictly Confidential* F501-0-1–5 SAP Template Page 15 of 34

Date: 27MAY2021

CT-AMT-060-01 EudraCT No.: 2013-005579-42 Statistical Analysis Plan Final no. 05 Page 16 of 34

## 4.3.4.3 Bleeding History from one year prior to screening

In a specific CRF module data regarding all bleeding episodes occuring in the one year period prior to the screening visit wil be registered. For each bleeding the following data will be recorded:

- Date of the bleed
- Type of bleeding (spontaneous, traumatic, unknown)
- If FIX replaceent therapy was used the name of the therapy and the total dose

These data will be listed and summarized as described in section 4.4.2.2 and 4.4.2.3. All data registered in the above mentioned CRF module will be included even if not complying strictly with the requirement of having occurred within one year (365 days) before the screening (Visit 1) date.

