14.2.2 Secondary Efficacy Endpoint Analysis

FIX Levels in Plasma

Data will be presented by subject, time point and dose level as summary tables and graphically.

Adjustment for time since most recent administration of FIX replacement therapy may be made, for example reporting by time less than 72 hours versus more than 72 hours after (reflecting prophylaxis free assessment). If applicable, the presentation will include summary statistics and confidence intervals for difference in FIX concentration between time-periods.

If applicable, the FIX level will be analysed using Non-Linear Mixed Models, possibly after transforming the data, and may include subject level random effect or subject level covariate to describe dependency between measurements. The analysis may include information on dose and timing of FIX replacement therapy. If relevant, the analysis may be extended to include modelling of values below lower level of quantification. The modelling may include subject level information on type of FIX replacement therapy, half-life, and if available previous knowledge of subject specific half-life for the FIX replacement therapy.

Number, Severity and Type of Bleeding Episodes

Bleeding episodes will be summarized by subject and overall, and will include number, duration and severity. Separate summaries may be made for bleeds depending on type and location, including target joints, and also summaries excluding recurrent bleeds.

Annualized bleeding rates overall and by severity will be presented. If relevant, summaries will be made using timing representing subject specific periods for pre-tapering, tapering period, and post tapering period until 26 weeks, and post 26 weeks.

Furthermore, the number of bleedings may be analysed using models for count data adjusting for time at risk using generalized linear model with Poisson or Negative Binomial distribution. Where description of timing and inter-event duration is of interest, models for time-to-event analysis may be used, such as Cox Proportional models or other parametric model, possibly including subject level frailty parameter. The analysis may include information on dose and timing of FIX replacement treatment, and measured FIX concentration.

Prophylactic and On-demand FIX Replacement Therapy

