## 4.4.2.2 Number, Severity and Type of Bleeding Episodes

In relation to the efficacy variables defined in this section and in section 4.4.2.3 a specific subset of the post-treatment period will be considered.

Larix A/S - Strictly Confidential F501-0-1–5 SAP Template Page 17 of 34 Date: 27MAY2021

Final no. 05

Page 18 of 34

CT-AMT-060-01 EudraCT No.: 2013-005579-42 Statistical Analysis Plan

For the interim analyses described in section 5 the end of this specific post treatment will simply be the specified cut-off date. For the final analysis, this will be the end of study date.

The start of this period is defined for each patient as the end of tapering, i.e. the date of the last prophylactic FIX replacement therapy administered. Before the data base freeze for an interim analysis in question (c.f. section 5) this start date will be decided on for each patient. The decisions made in connections with the first formal interim analysis (c.f. section 5) appear in Appendix 2.

As mentioned in section 4.3.4.3 all bleeding episodes occurring in the one year period prior to screening will be registered.

These data will be presented in a listing and also summarized with respect to annualized bleeding rate, and number of episodes. Separate summaries will be generated for all bleeds and for the different types of bleeds (spontaneous, traumatic, unknown, spontaneous+unknown). It is assumed that the bleeding episodes are observed during exactly one year i.e. the observed number bleeds will correspond exactly to the annualized bleeding rate for the 1 year prior to screening data for each patient.

From Visit 1 and throughout the entire trial participation period, patients will be asked to record information on bleeding episodes in an e-diary.

The patient e-diary will include questions regarding each bleeding episode with respect to

- Date and time of onset of bleed
- Date and time of stop of bleed
- Location of bleed (a number of categories have been defined in e-diary/eCRF)
- Circumstances of bleed (spontaneous, traumatic, minor surgery see definitions in protocol section 12.12)
- FIX replacement treatment of bleed (medication, dose, date and time of administration)
- Other therapy (pain relieving medication compression, ice)
- Investigator's evaluation of severity of bleed
- Evaluation of effect of treatment by patient (excellent, good, moderate, none), see definitions in protocol section 12.1.2)

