- Evaluation of effect of treatment by investigator (excellent, good, moderate, none), in case bleeding episode requires hospitalisation or have a fatal outcome. It is noted that this assessment is registered on the (S)AE form.

It is noted that according to the protocol section 12.1.2 a bleeding episode is defined as a recurrent episode (re-bleed) if it is a worsening of symptoms in the same location after an initial period of improvement, either on treatment or within 72 hours after stopping treatment. If a bleed occurs in the same location later than 72 hours after stopping, the bleed is considered as a new bleed.

It is noted that a registration is made in the e-diary for each location for each bleeding episode i.e. if a bleeding episode occurs with more than one location this will be registered with multiple entries (one for each location) in the e-diary. Such multiple entries will be considered as separate bleeding episodes.

All the diary data and evaluations by the patient and investigator will be listed.

All bleeding episodes requiring FIX treatment from the post tapering period (end of prophylactic treatment until cut-off or end of trial) will be summarized in a similar same way as the bleeding episodes from the 1 year prior to screening period, with descriptive summaries of mean observation period and total observation period added. Total observation period (years) for each cohort is calculated as the sum of the observation periods of all patients in that cohort.

Larix A/S - Strictly Confidential F501-0-1–5 SAP Template Page 18 of 34

larix

Sponsor: uniQure

Date: 27MAY2021

CT-AMT-060-01 EudraCT No.: 2013-005579-42 Statistical Analysis Plan Final no. 05 Page 19 of 34

For this period the annualized bleeding rate is calculated as (number of bleeds \* 365.25)/ number of days in the period from last prophylactic dose until cut-off (or end of trial).

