## 4.4.2.3 Prophylactic and On-demand FIX Replacement Therapy

As mentioned in section 4.3.4.3 administration on demand FIX replacement therapy in the 1 year period prior to screening has been registered. All these data will be listed. The on-demand FIX replacement therapy products used and the total dose used will be summarised for each cohort for this 1 year period prior to screening.

From Visit 1 and throughout the entire trial participation period, patients have been asked to document use of FIX replacement therapy in an e-diary. Two different modules in the e-diary will be used for registering prophylactic and on-demand FIX replacement therapy respectively.

The patient e-diary modules will include questions with respect to

- Date/time of administration
- Drug name
- Dose

All data will be presented in listings. The listings will be split two parts: a) the period from screening and until the end of tapering b) the period from end of tapering until end of trial/cut-off date in an interim analysis.

The use of prophylaxis and on-demand treatment in general will be summarized according to product and type (on-demand or prophylaxis). The summarises will be performed by cohort and overall. Furthermore, the total on-demand use for each patient (regardless of product) for the post tapering period will be summarized by cohort. The total dose for each patient will be annualized i.e. the dose will be adjusted for the length of the observation time (end of tapering until end of trial/cut-off date in an interim analysis) for the patient in question.

A listing will be generated combining on a patient level the information for the 1-year period prior to screening and for the post tapering-period including on-demand FIX-replacement therapy (annualized), bleeding episodes and annualized bleeding rates.

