# 7 Tables, Listings and Figures

The shell listings, tables, and figures generated appear in the two shell documents (CT\_AMT\_060\_01\_Table\_Shells\_v05.docx and CT\_AMT\_060\_01\_Listing\_Shells\_v05.docx) attached to this SAP. The two documents are considered as being a part of this SAP.

Larix A/S - Strictly Confidential F501-0-1–5 SAP Template Page 30 of 34

Date: 27MAY2021

CT-AMT-060-01 EudraCT No.: 2013-005579-42

Statistical Analysis Plan

Final no. 05 Page 31 of 34

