N: Number of patients in Full Analysis Set (FAS). n: Number of patients with at least one dose of medication. Cohort 1: AAV5-hFIX 5.0 x 10^12 gc/kg, Cohort 2: AAV5-hFIX 2.0 x 10^13 gc/kg

Sponsor: uniQure biopharma B.V		Date 27MAY2021		larix
Trial ID: CT-AMT-060-01 EudraCT No: 2013-00557942-42		Table Shells		Final Version 05 Page 19 of 66
Table 14.2.7 Summary of post-treatment	t use of FIX replace	ment therapy - On-Dema	and - Period: From Dosing To cut	-off - FAS
	Cohort 1 (N=x)	Cohort 2 (N=x)	Total (N=x)	
Use of on-demand FIX replacement therapy	n (%)	n (%)	n (%)	
Any medication	x (xx.x)	x (xx.x)	x (xx.x)	
Benefix	x (xx.x)	x (xx.x)	x (xx.x)	
Haemonine	x (xx.x)	x (xx.x)	x (xx.x)	
Mononine	x (xx.x)	x (xx.x)	x (xx.x)	
Etc.				
Repeat for all medications reported				

N: Number of patients in Full Analysis Set (FAS). n: Number of patients with at least one dose of medication. Cohort 1: AAV5-hFIX 5.0 x 10^12 gc/kg, Cohort 2: AAV5-hFIX 2.0 x 10^13 gc/kg

Sponsor: uniQure biopharma B.V		Date 27MAY2021		larix
Trial ID: CT-AMT-060-01 EudraCT No: 2013-00557942-42		Table Shells		Final Version 05 Page 20 of 66
Table 14.2.8 Summary o	f FIX replacement therapy d	lose - Period: One year prior t	o screening - FAS	
	Cohort 1 (N=x)	Cohort 2 (N=x)	Total (N=x)	
FIX Infusions (IU/year)				
n	x	x	x	
Mean (SD)	xxx (xxx)	xxx (xxx)	xxx (xxx)	
Median	XXX	XXX	XXX	
Min ; Max	xxx ; xxx	xxx ; xxx	xxx ; xxx	

N: Number of patients in Full Analysis Set (FAS). n: Number of patients with at least one dose of medication. Cohort 1: AAV5-hFIX 5.0 x 10^12 gc/kg, Cohort 2: AAV5-hFIX 2.0 x 10^13 gc/kg FIX infusions is the total sum of FIX administrated as prophylaxis and On-demand.

Sponsor: uniQure biopharma B.V		Date 27MAY2021		larix
Trial ID: CT-AMT-060-01 EudraCT No: 2013-00557942-42		Table Shells		Final Version 05 Page 21 of 66
Table 14.2.9 Summary of	FIX replacement therapy d	lose - Period: From tapering-o	ff to cut-off - FAS	
	Cohort 1 (N=x)	Cohort 2 (N=x)	Total (N=x)	
Annualized FIX Infusions (IU/yea	r)			
n	х	x	х	
Mean (SD)	xxx (xxx)	xxx (xxx)	xxx (xxx)	
Median	XXX	XXX	XXX	
Min ; Max	xxx ; xxx	xxx ; xxx	xxx ; xxx	

N: Number of patients in Full Analysis Set (FAS). n: Number of patients with at least one dose of medication. Cohort 1: AAV5-hFIX 5.0 x 10^12 gc/kg, Cohort 2: AAV5-hFIX 2.0 x 10^13 gc/kg FIX infusions is the total sum of FIX administrated as prophylaxis and On-demand.

Sponsor: uniQure biopharma B.V	Date 27MAY2021			larix

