Trial ID: CT-AMT-060-01 EudraCT No: 2013-00557942-42	Та	able Shells		Final Version 05 Page 22 of 66
Table 14.2.10 Summary of bleeding episode	s and annualized bleedin	g rates - All bleeds - Per	iod: One year prior to screening - FAS	6
	Cohort 1 (N=x) n (%)	Cohort 2 (N=x) n (%)	Total (N=x) n (%)	
Number of patients with bleed, n (%)	x (xx.x)	x (xx.x)	x (xx.x)	
Number of bleeds	x	x	x	
Bleeds per patient (min; max)	x; x	x; x	x; x	
Annualized bleeding rate				
n	х	х	x	
Mean (SD)	x.xx (x.xx)	x.xx (x.xx)	x.xx (x.xx)	
Median	x.xx	x.xx	X.XX	
Min ; Max	x.x; x.x	x.x; x.x	x.x; x.x	

N: Number of patients in Full Analysis Set (FAS). n: Number of patients with the parameter. SD: Standard Deviation. n\*: Number of bleeds. Severity: Assessment by investigator.

Cohort 1: AAV5-hFIX 5.0 x 10^12 gc/kg, Cohort 2: AAV5-hFIX 2.0 x 10^13 gc/kg

Only bleeds requiring on demand FIX infusion are included.

Sponsor: uniQure biopharma B.V	Date		larix	
Trial ID: CT-AMT-060-01 EudraCT No: 2013-00557942-42	Та	ble Shells		Final Version 05 Page 23 of 66
Table 14.2.11 Summary of bleeding episodes	and annualized bleeding	g rates - Spontaneous ble	eeds - Period: One year prior to screen	ing - FAS
_	Cohort 1 (N=x) n (%)	Cohort 2 (N=x) n (%)	Total (N=x) n (%)	
Number of patients with bleed, n (%)	x (xx.x)	x (xx.x)	x (xx.x)	
Number of bleeds	х	х	х	
Bleeds per patient (min; max)	x; x	x; x	x; x	
Annualized bleeding rate				
n	х	х	x	
Mean (SD)	x.xx (x.xx)	x.xx (x.xx)	x.xx (x.xx)	
Median	X.XX	x.xx	X.XX	
Min ; Max	x.x; x.x	x.x; x.x	x.x; x.x	

N: Number of patients in Full Analysis Set (FAS). n: Number of patients with the parameter. SD: Standard Deviation. n\*: Number of bleeds. Severity: Assessment by investigator.

Cohort 1: AAV5-hFIX 5.0 x 10^12 gc/kg, Cohort 2: AAV5-hFIX 2.0 x 10^13 gc/kg

Only bleeds requiring on demand FIX infusion are included.

Sponsor: uniQure biopharma B.V	Date 27MAY2021			larix
Trial ID: CT-AMT-060-01 EudraCT No: 2013-00557942-42	Та	ble Shells		Final Version 05 Page 24 of 66
Table 14.2.12 Summary of bleeding episodes	and annualized bleeding	g rates - Traumatic bleed	ds - Period: One year prior to screening	- FAS
	Cohort 1 (N=x) n (%)	Cohort 2 (N=x) n (%)	Total (N=x) n (%)	
Number of natients with bleed n (%)	x (xx x)	x (xx x)	x (xx x)	
Number of bleeds	X	X	x	
Bleeds per patient (min; max)	x; x	x; x	x; x	
Annualized bleeding rate				
n	х	х	x	
Mean (SD)	x.xx (x.xx)	x.xx (x.xx)	x.xx (x.xx)	
Median	x.xx	x.xx	X.XX	
Min ; Max	x.x; x.x	x.x; x.x	x.x; x.x	

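### The prior-year bleeding rate counts FIX-treated bleeds from outside the 365-day window but divides by exactly one year, so any such record can only raise the baseline

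*SAP*

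**What the plan says.** SAP 4.3.4.3 describes a CRF module for bleeds in the year before screening, recording for each the date, the type and any FIX product with its total dose. The records feed the bleeding-rate summaries of 4.4.2.2 as well as the FIX-use summaries of 4.4.2.3. Nothing is filtered by date: whatever was "registered in the above mentioned CRF module will be included even if not complying strictly with the requirement of having occurred within one year". The SAP defines that year as 365 days, counted back from Visit 1.

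SAP 4.4.2.2 sets the time base for this period: "It is assumed that the bleeding episodes are observed during exactly one year i.e. the observed number bleeds will correspond exactly". Each patient's count is therefore his ABR. For the post-tapering period the same section multiplies the number of bleeds by 365.25 and divides by the "number of days in the period from last prophylactic dose until cut-off (or end of trial").

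The footnotes to Tables 14.2.10 to 14.2.14 narrow the count: "Only bleeds requiring on demand FIX infusion are included". SAP section 7 makes the shells binding: "The two documents are considered as being a part of this SAP".

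SAP 4.4.2.3 also plans a listing "combining on a patient level the information for the 1-year period prior to screening and for the post tapering-period", covering annualized on-demand FIX use, bleeds and ABRs.

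**The concern.** The numerator is open-ended and the denominator is fixed. A FIX-treated bleed dated outside the 365 days counts as if it had happened within them. SAP 4.1 and Protocol 14.2 both say that patient-level summaries, naming the ABR, are adjusted for observation time. The post-tapering rate follows that principle. The prior-year rate does not once an out-of-window record is present.

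Bleeding rate is a supportive efficacy endpoint and the trial has no control group, so the prior year serves as the comparator. Readers will set Tables 14.2.10–14.2.14 against Tables 14.2.15–14.2.19, and the combined listing sets the two periods together for each patient. An inflated baseline makes any fall in bleeding look larger. The dose of each such bleed also enters the on-demand part of prior-year FIX use.

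Protocol 14.2.2 leaves room for another reference period ("If relevant, summaries will be made using timing representing subject specific periods for pre-tapering, tapering period"), but the table shells contain no such summary. The prior-year rate is the only pre-treatment bleeding rate with a table shell.

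**Working it through.** The plan gives no figure to reproduce: there is no sample-size formula, no hypothesis test and no count of out-of-window records. The check is arithmetic on the SAP's own rule.

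**Inputs.** For one patient, let *a* be the FIX-treated bleeds inside the 365 days before Visit 1 and *k* the FIX-treated bleeds recorded outside them. Both are unknown, so the values below are assumed. Cohort size is 5 (SAP 2.1), or up to 7 in Cohort 2 (Protocol 9.1).

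**Formulas.**
- SAP rule: ABR = (*a* + *k*) / 1 year
- Strict 365-day rule: ABR = *a* / 1 year
- Difference: *k*, which is never negative

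**Absolute effect of one record (*k* = 1).**
- Patient ABR: +1.0
- Cohort mean: 1/5 = +0.20, or 1/7 = +0.14 with 7 patients
- Cohort median: may stay the same but cannot fall

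**Relative effect of one record on that patient's baseline (1/*a*).**
- *a* = 4: 1/4 = 25%
- *a* = 8: 1/8 = 12.5%
- *a* = 12: 1/12 = 8.3%

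**Illustrative pre/post contrast.** The SAP defines no percent reduction; this only shows the scale.
- *a* = 4, post-tapering ABR 2: true reduction 1 − 2/4 = 50%; apparent reduction 1 − 2/5 = 60%
- *a* = 12, post-tapering ABR 6: true reduction 1 − 6/12 = 50%; apparent reduction 1 − 6/13 = 53.8%

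**Alternative reading.** Suppose the site simply looked back further, over *W* days, and all bleeds in that span are valid. The correct rate is then (*a* + *k*) × 365.25 / *W*. For *a* = 4 and *k* = 1 the SAP gives 5:
- *W* = 380: 5 × 365.25/380 = 4.81, so the SAP is 4.0% too high
- *W* = 400: 5 × 365.25/400 = 4.57, so the SAP is 9.5% too high
- *W* = 456: 5 × 365.25/456 = 4.00, so the SAP is 24.8% too high

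The bias is smaller on this reading but always upward when *W* exceeds 365.25.

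**Scope limits.** Untreated out-of-window bleeds do not enter Tables 14.2.10–14.2.14. The percentages do not carry over to total IU per year, because the footnote to Table 14.2.8 says "FIX infusions is the total sum of FIX administrated as prophylaxis and On-demand"; only the on-demand part is affected.

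**The case against.** The strongest reply is that the effect may be nil. The module is meant for the one-year period, and nothing in the documents shows that a stray record exists. That is correct, and the size stays conditional on it.

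Second, the 25% figure treats an out-of-window bleed as wholly spurious. With a longer look-back and a matching denominator, the overstatement could be only 4.0% to 9.5% for a look-back of 380 to 400 days. With a post-tapering ABR of 2, the 60% apparent reduction would then compare with 58.4% (1 − 2/4.81) or 56.2% (1 − 2/4.57), not with 50%. This limits the size but leaves the direction unchanged. The 365-day window is the one the SAP itself names.

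Third, the rule is open and deliberate: it is stated in the text, and the change log for edition 04 records that it was emphasised. The analysis is descriptive, and the dated bleeds are listed, so a reader could rebuild the rate. This removes any question of type I error or concealment. The tables and the combined listing would still carry the unfiltered figure, and the plan gives no filter, adjusted denominator or sensitivity row. The pages for the listing shells were removed from the public copy, so a flag there cannot be ruled out.

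Fourth, other pre-treatment data exist: a 12-month count by regimen (SAP 4.3.4.2) and bleeds from screening to dosing (Listing 16.2.6.1). They are a partial cross-check. They are listed, not summarized as a rate, and 4.3.4.2 has the same inclusion rule.

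**Conclusion.** The concern holds. SAP 4.3.4.3 and 4.4.2.2 together pair an open numerator with a fixed one-year denominator. Any FIX-treated out-of-window record raises the patient's baseline ABR and the cohort mean, and can never lower either, so the error favours the product. Against the SAP's own 365-day window, each record adds 1.0 to the patient and 0.20 (or 0.14) to the cohort mean. The relative overstatement of 8.3% to 25% rests on an assumed 4 to 12 in-window bleeds, and a matched look-back could make it smaller. The number of such records is not given and may be zero. The point should be settled before the final tables are produced. It affects a descriptive comparison of a supportive endpoint and not the primary safety endpoint.

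**What to change.** For the final analysis:

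- Compute the prior-year ABR and on-demand IU only from FIX-treated bleeds dated within the 365 days before Visit 1.
- State a rule for partial dates, for example to count a bleed only if every date it could have falls inside the window. This can drop a genuine in-window bleed, but it is in keeping with the conservative approach to partial dates in Protocol 14.6.1.
- Show the unfiltered figure beside the filtered one. The pair shows how much the out-of-window and partly dated records matter, and the unfiltered figure traces back to the interim report.
- Flag the out-of-window records and list them separately. If there are none, say so in a footnote.

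Dividing by the actual look-back would also be coherent, but look-back length is not among the module items that the SAP names. Bleed date and FIX dose are, so the filter needs no new data.

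The cost is a change of SAP wording, one date filter and one extra row or column in the prior-year tables. The baseline, and so the apparent reduction, may be smaller. It may also differ from the interim clinical study report, whose data Protocol 20.1 treats as locked, and the difference would need a short explanation.
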